1. Hiring of personnel (Months 1 – 2)
2. Kick-off meeting with clinical partners (Month 2): The PI will update a trauma-informed care (TIC) workgroup, already convened in 2019 and meeting bi-monthly, about funding of this project. The group will plan for the implementation mapping sessions that will be scheduled (Months 2-5) of the study.
3. Kick-off meeting with research team (Month 2): The PI will hold a kick-off meeting with the research team (including consultants)
4. Preparation for Step 1 of trial period (Months 4-6):
 - 4.1 Month 1 or 2: The Research Director at the FQHC will receive the implementation coaching training online (scheduled for May of 2021 by the organization providing the national certification training). Due to very high clinic staff turnover, we are broadening the potential training options for implementation coaching and by including more individuals (e.g., clinic screeners, managers, director of Healthy Steps program).
 - 4.2 Months 3-5: [name] will randomly select five clinics (from a pool of 27 clinics) as research sites for the study.
 - 4.3 Months 2-4: [name] will create a secure Research Electronic Data Capture (REDCap) web application database, which is HIPAA-compliant, and develop an algorithm that will include the questions for each ACEs screening tools (PEARLS and PSC) and an ACEs-related health conditions checklist provided by the state of California as a checklist. The algorithm will automatically provide an assessment of the child patient's risk level for ACEs-related health issues, as well as indicate whether a referral to mental-health services is indicated.
 - 4.4 Months 5 - 7: Pilot testing of the REDCap algorithm using computer tablets by the PI, [name] and the FQHC's data analyst and with the use of dummy data. We will also use simulations/demos with the Community Advisory Board to reduce clinical burden. Test data will be entered into the REDCap system to identify glitches and refine the system as necessary.
 - 4.5 Months 5-7: ACEs computer tablets delivered to the Research Director ([name]) via FedEx and for distribution to each of the selected clinics. Each clinic's manager will be responsible for delivering the tablets to the assigned ACEs screener for the study. Zoom conferences will be held with the principal investigator (PI), FQHC implementation coach and screeners to familiarize them with the tablets and how to operate them, and troubleshoot any potential problems.
 - 4.6 Month 4: The PI and consultant ([name]) will pre-record 3 video-training sessions on study procedures and protocols, caregiver consent process and administration of the PSC survey (in 2020, all clinic personnel at the FQHC partner have already completed a 2-hour online training on how to administer the PEARLS screener)

- 4.7 Month 5: Screeners at each selected clinic will go over the videos for training. The PI and [name] will schedule a follow up 45-min call with each screener to discuss videos and learning/questions.
- 4.8 Months 6 – 7.5: Baseline starts in all five selected clinics. Pre-intervention data will be collected from the clinics over a 10-week period. Clinic staff will be told to follow the ACEs state requirements, which include the PEARLS screenings, ACEs-related health conditions checklist, wellness exam, follow-up education, and mental-health referrals if deemed appropriate. Mediators data will be collected at the end of this period.
- 4.9 Months 7.5 to 30 / Trial starts:
 - 4.9.1 During a 10-week trial period for each clinic (data collection will continue until the end of the trial), each clinic switching from control to intervention status will start using the implementation strategies (i.e., support from the trained implementation coach, TIC workgroup guidance/advise, use of electronic tablets for screenings and service referrals).
 - 4.9.2 Due to the human and financial impact of COVID-19 epidemic, the randomized control clinics had not implemented ACEs screening at the time of the pilot starting. We have identified two clinics within the healthcare system, not part of the trial, that have started implementing ACEs screening. These two clinics will serve as non-randomized comparison groups for this study. We will compare our study clinics and these comparison clinics on ACEs screenings and on referrals to mental health services.
 - 4.9.3 Steps for ACEs screenings with caregivers:
 - 4.9.3.a. When a child and their caregiver come to the clinic for the wellness visit, screening staff will conduct the study screenings using a tablet device that has the REDCap database on it. This should take 10 minutes.
 - 4.9.3.b. As part of the screenings for the study, screening staff will use either the Baby Pediatric Symptoms Checklist (BPSC) or the Preschool PSC based on the child's age to help caregivers more accurately identify perceived behavioral and/or emotional concerns they have about their child. Due to low reading levels among some of our participants, the screener will ask caregivers if they prefer the questions to be read to them by the screener.
 - 4.9.3.c. Once the staff has finished conducting the screenings (i.e., PEARLS and the BPSC or PPSC), the physician will come in to conduct the wellness visit as part of routine care. The physician will use the tablet provided by the screening staff with the REDCap database to check ACES-related health conditions from an automated checklist.
 - 4.9.3.d. Based on our REDCap preprogrammed algorithm, which takes the information from the PEARLS, PSC, and the ACES-related health condition checklist, a pop-up box will appear indicating the child's risk level (low/medium/high). If the child's risk level is determined to be high, the physician will be prompted on the tablet to begin a mental-health referral for the child and the caregiver.
 - 4.9.3.e. Screening staff will document when any caregivers decline screenings, or when there is an incomplete screening for any reason.
 - 4.9.3.e.1 Mediators and primary and secondary outcomes will be collected by the co-leads at the FQHC, the PI and the study

coordinator.

- 4.9.3.e.2 During this time period, EMR data will be pulled by the FQHC's data manager and provided to the PI as excel tables and using a password protected and encrypted email. The following data will be collected from REDCap and from the data manager (EHR records): number of eligible child visits, number of PEARLS and BPSC/PPSC screenings and scores, eligible children who are referred to services, child characteristics, and number of mental health referrals.

4.9.3e.3 At the end of each 10-week trial period, the principal investigator and study statistician will meet to review the REDCap system and will follow up with clinical partners to discuss any questions and unexpected data patterns.

4.10 Months 12-30: An online survey with demographic and survey questions on feasibility, acceptability, and implementation leadership and climate measures will be sent out to clinic staff, managers, and primary-care providers using work emails. Follow up interviews will be conducted on the phone.

4.11 Months 8 – 36: The study's data analyst will lead data preparation and analysis and will meet weekly with the PI, research team and clinical partners to go over progress and troubleshoot.

4.12 Months 22-42: Preparation of the R01 proposal and sharing of results with clinical partners. Dissemination of results.

See a timeline summary table of the trial activities below:

2. The intervention will be implemented at five partner FQHC clinics. Handheld computer tablets will be provided to clinic screening staff with the REDCap web application database (implementation strategy). The tablets will enable clinic screening staff to administer the PEARLS and BPSC/PPSC assessments by the medical assistant (screener) to the caregiver of the child patient prior to the wellness visit. After these assessments have been conducted using the tablet, the screening staff will hand the tablet to the primary-care provider. The tablet will then guide the primary-care provider to complete the ACEs-related conditions checklist provided by the state. The REDCap web application algorithm will use the information from the PEARLS, PSC and ACEs-related health

conditions checklist to determine whether the child is deemed to be at low, medium, or high risk for toxic stress and/or caregiver concerns about the child's emotional/behavioral development. If the child is determined to be at high risk, the web application will prompt the primary-care provider to make a referral to mental-health and support services.

3. Steps that will be taken to protect participant privacy and confidentiality:

For child data - Anonymous: A unique study identifier will be linked to child patient's electronic medical record chart ID. The REDCap secure web application will be used to implement the screening process and will store data associated with screening tools, using study identifiers. In addition, in order to provide patient information to NIMH for the data sharing requirement, we will collect the following information from each child patient: child's date of birth (we will obtain this information from the EMR records and per caregiver signed consent and HIPAA released forms), and the child's city of birth and name (asked of caregiver during the screening and using the REDCap system). This information will only be used to meet NIMH data sharing requirement and destroyed after we meet this requirement. This information will not be retained by NIMH because their system will use the identifiers to create a unique participant number. We will use study ID for each participant for most of the work. We will keep identifiers in a separate password-protected folder in the study OneDrive. This information will not be kept in the REDCap forms. We will retrieve additional information from children screened in REDCap by producing a report in REDCap with a list of children screened by record number and by medical chart number. Then, the Borrego Health co-lead persons will access that list of children directly from REDCap using a password-protected user account, and will share the list internally with the data manager co-lead for linkage to additional data. Then, the data manager will share with the study PI the data for each child on that list using a password-protected excel file, and send using a password-protected and encrypted work email. Data on the control/comparison clinics will be reported using aggregated numbers and using the same data retrieval procedure. Recordings of interviews will be kept in a password-protected computer drive and they will be destroyed after the transcription has been finalized. All transcriptions will not include individual names or identifiable information. All data, including transcriptions, will be kept for 3 years, and then erased per NIMH policy.

Reporting on adverse events: This study does not involve physical/psychological harm. Screeners at the clinics will receive training in-person or virtual on identifying adverse events related to the consenting of participants and adherence to study activities and procedures. Written information is also included in the study manual shared with the care team at each participating clinic. Any deviations from study protocol will be reported to the PI within 24 hours.

For child patient and clinic staff information

- 1. Data storage plans:** All data will be entered into a password protected VPN Egnyte system at the University of Colorado, Denver (UCD) and only clinic and participant IDs will be used to protect confidentiality. EMR data will be entered by medical personnel at each clinic and into a secured i2iTracks/Tableau centralized dashboard within the FQHC secured network. To protect confidentiality, all data will be shared with the UCD research team following guidelines from a signed Data Transfer Agreement (DTA), and after IRB approval. The PI and the data analyst at UCD will log in into a secured shared drive to access the data (i.e., Egnyte). The clinic personnel survey and interview transcripts will not contain identifying information. The survey will be distributed through a HIPAA compliant REDCap account or through a UCD's Qualtrics account. No participant data will be stored in clinics' iPads. Data will automatically be stored in UCD's REDCap system. The EMR data will contain the child's chart ID

so we can link that data with the child's ACEs screening data entered into the REDCap tablets. Once the files are linked, we will only use the child's study ID and will delete the child's chart ID from the files. When an internet connection is available, data is transmitted directly to REDCap using a SSL (TLS v1.2) connection. A hash-based message authentication code (HMAC) is used to verify the integrity of the data and to authenticate the sender. Participant entered data (i.e. task responses) are not stored or sent anywhere else. Data exists on the REDCap tablet device or on the UCD server. Data is wiped from the device after the MyCap app verifies that data has been successfully transmitted. By default, data is wiped.

We are clarifying that clinic staff access to the REDCap system for the study will be done through remote access by using a link and a password protected login system and only for data entry. No data will be saved in the computer tablet used to access REDCap and clinic personnel will not have access to all study data.

Results of the REDCap screenings will be kept in clinical records and for a group of children (n= 450) it will be kept in the REDCap system for research.

2. Plans for dissemination of findings/results: The PI will ensure the clinical trial under this R21 award upon funding is registered and results information is submitted to ClinicalTrials.gov and to meet NIH policy on dissemination of NIH-funded clinical trial information (<https://grants.nih.gov/policy/clinical-trials/reporting/understanding/nih-policy.htm>). The UCD system also has internal policies in place to ensure that clinical trials registration and results in reporting occur in compliance with NIH policy requirements. The PI will be responsible for submitting the protocol and the results to the website. Informed consent documents for the clinical trial will include a specific statement relating to the posting of clinical trial information at ClinicalTrials.gov. In December of 2021, we published the study protocol in a peer-reviewed journal - *Implementation Science Communications*. To facilitate replication in other studies, most measures we propose to use are available in the public domain as standard measures in pediatric settings (i.e., PSC), as well as implementation measures (leadership, climate, reach, feasibility, and acceptability). In addition, we will submit the study results to ClinicalTrials.gov and any updates to the study description of the page as needed. The PI will present findings to leading conferences from academic societies such as: Academy Health, the Society for Implementation Research Collaboration (SIRC), the Society for Social Work and Research (SSWR), and the Science of Dissemination and Implementation in Health (D&I). Besides conference presentations, we will draft and submit at least three manuscripts for peer review in professional publication: (1) study protocol paper (completed), (2) conceptual paper on the use of EPIS framework to guide an intervention mapping process (under review), (3) pilot stepped-wedge randomized trial study main effects, and (4) mechanisms of change of policy interventions in Federally Qualified Health Centers manuscripts.

b. Instrumentation

b.i. **Questionnaires/Survey Measures for the study (names and citations):**

- The Pediatric Symptoms Checklist is comprised of two measures based on age:
 - The Baby Pediatric Symptom Checklist (BPSC) is a 12-item screening measuring children's psychosocial function validated for children ages 0-18 months. Cronbach's alpha adequate for subscales (alpha=0.75 to 0.83).
 - The Preschool Pediatric Symptom Checklist (PPSC) is an 18-item screening for measuring children's psychosocial functioning validated for children ages 18-60 months. (alpha=0.92)

- The Feasibility of Intervention Measure (FIM) is a self-reported 4-item instrument to evaluate feasibility of implementation efforts. Good internal consistency (alpha =0.89). Test-retest reliability (r=0.88).
- The Acceptability of Intervention Measure (AIM) is a 4-item instrument to evaluate acceptability of implementation efforts. Good internal consistency (alpha =0.83). Test-retest reliability (r=0.83).
- Fidelity checklist form will be developed by principal investigator and [name].
- Implementation Leadership Scale is a 12-item scale with four subscales measuring proactive leadership, knowledgeable leadership, supportive leadership, and perseverant leadership. Reliability for the total scale is strong (alpha=0.98).
- Implementation Climate Scale is a 6-item scale measuring the strategic climate for the implementation of interventions.
- Readiness for Change is a 12-item scale measuring clinic staff and supervisors' perceptions of how prepared they are to start the ACEs screenings. This measure is only used at baseline for all clinics (Step 1 in the Stepped Wedge Design schedule).

b.ii. Qualitative instruments:

We will use a semi-structure interview protocols for Aim 2 in interviews with clinic personnel and with caregivers. We will allow participants to add in relevant areas of discussion. Each interview protocol has been uploaded to the IRB application.

c. Data Analysis

Quantitative data: We will use descriptive statistics (i.e., frequencies, means and standard deviation estimates) to describe the analytical sample. We will examine whether the implementation strategies (i.e., advisory board, use of REDCap handheld tablets, use of the PSC tool and an implementation coach) increases the number of children screened and referred to support services, compared to baseline. To do that, we will use methodology that accounts for repeated measures over time and that accounts for both within-person and across-person variation (i.e., Generalized linear mixed model (GLMM)) while controlling for clustering of patients within clinics and possible confounding by calendar time. *Our analysis will include sex as a biological variable, testing for a differential effect on outcomes by child sex.* We will report the magnitude of missing data and compare demographic and clinic characteristics and outcomes between observations with versus without missing data. In sensitivity analyses, we will perform multiple calculations (i.e., imputations) using fully conditional specification to obtain 10 complete datasets; summary estimates of intervention effects with 95% confidence limits over the 10 datasets will incorporate within- and between-dataset sampling variability.

Comparison of randomized intervention sites to non-randomized control sites

Due to the human and financial impact of COVID-19 epidemic, the randomized control periods had not implemented ACEs screening at the time of the pilot starting. We have identified two clinics that have implemented ACEs screening that are not part of the trial.

To obtain an additional non-randomized estimate of the intervention effect, we will compare:

- (1) the control periods in the randomized clinics to comparable time periods in the non-randomized clinics;
- (2) the intervention periods in the randomized clinics to comparable time periods in the non-randomized clinics.

We will use the same GLMM models as described above, with indicator variables for non-randomized vs randomized clinic, and randomized control vs intervention periods. Groups will be compared on ACEs screenings, and mental health referral rates.

Qualitative data: All interviews will be audio-taped and professionally transcribed. Data analysis will include coding transcripts to identify common themes, capture analytical categories from the emerging themes, and depict associations between categories. Interviews will be transcribed using pseudonyms to increase confidentiality. Two coders (study team member and graduate student) will analyze data. *Inter-rate reliability (IRR) will be calculated as the proportion of agreed codes over the total number of codes in the document* using Microsoft Word (Word) and Excel. Rigor strategies include documenting coding decisions and thematic development. A detailed codebook will be developed.

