- 2) Non-English-Speaking Caregivers: For Aim 2, we will randomly select caregivers at each clinic whose children were screened for ACEs to participate in phone interviews about their perceptions of the screening process. We will also gather basic caregiver sociodemographic information (age, gender, education). Spanish-speaking caregivers will be interviewed by a fluent Spanish speaker (e.g., The PI is Latinx scholar and Spanish is her first language). For the child screenings (Aim 1), we will follow the clinics' procedure. That is, when the caregiver makes an appointment for their child, they are asked if they would like a translator. Every clinic has someone who speaks Spanish and two have someone who speaks Arabic. In the event that there would not be a Spanish-speaking staff member available, translation services are available.

IV. Recruitment/Screening Process (sampling strategy)

- a. Recruitment will take place at five Federally Qualified Health Center (FQHC) clinics located in under-resourced communities in California. We do not have exact locations yet because these five clinics will be randomly selected from a total of 28 clinics located in multiple counties (e.g., Riverside, San Bernardino, San Diego).
- b. Recruitment of caregivers for participation in the ACEs screenings and to allow access to their child's EMR data: Once the caregiver checks-in at the front desk, the medical assistant (MA) individual will meet the family and will walk them to the examination room for their wellness visit (part of routine care procedure). As part of this event, the MA will introduce the study and obtain consent from the caregiver for participation. Here, caregivers can decline, in which case the MA will continue with the wellness visit procedure that includes screening for ACEs using the PEARLS tool (this screening is happening at the clinics and regardless of this study). The FQHC's data analyst will receive the list of children who had been screened and consented to be in the study and will provide EMR data to the PI based on the study design schedule. Note: If the caregiver declines to participate in this study, the screener will not use the REDCap programmed tablets as we will not have that caregiver's screening data at all.

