Once the pilot study started, two randomly selected clinics were not able to participate - one clinic closed and one clinic lost their pediatrician leading ACEs screenings. Due to extremely high staff turnover at the clinics and among FQHC leadership, additional clinics selected were not able to participate in this research study. Thus, from the three clinics that finished the stepped wedge schedule, one was randomly selected and two clinics joined based on their capacity to participate in a research study at that time.

Eligible children were those aged 0-5, on public insurance, attending a wellness visit with the participating clinician.

Data sources:

Data for the primary outcomes, including reach of ACEs screenings and mental health referral rates, was obtained via the electronic medical record (EMR) at the partner health system. Additional data for secondary analyses was collected using REDCap among intervention patients only, including the PSC scores and ACEs screening results. See Figures 2 and 3 for the Consort tables.

Figure 2. CONSORT table for the study pilot study – Electronic Medical Records Data.

[figure not shown]

Figure 3. CONSORT table for sub-sample of data – REDCap system.

[figure not shown]

Table 1. Description of measures

Measure	Description/psychometrics	Source
ACEs Screening		
PEARLS¹ screening (ages 0-11)	Caregiver-reported tool (17-items) designed to identify exposure to childhood adversity and stress factors that may lead to toxic stress and negative health outcomes. Number of endorsed events are summed up (0-4+) to identify risk level for toxic stress and potential symptomatology. English/Spanish	Caregiver
ACEs associated health conditions²	State-sponsored list with 25 ACEs associated health conditions for children ages 0 – 5. ² Physical conditions include asthma, allergies, unexplained somatic symptoms such as headaches. Mental health related conditions (over 10) include aggression, depression, ADHD, and anxiety	EMR system

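### The protocol's randomized label is contradicted for two of the three study clinics and unsupported for crossover order

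*Protocol*

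**What the plan says.** **The label.** The protocol applies the word *randomized* to the study clinics and their periods in several places.
- Section V.1, step 4.9.2, says that "the randomized control clinics had not implemented ACEs screening at the time of the pilot starting".
- Section V.c, Data Analysis, has the heading "Comparison of randomized intervention sites to non-randomized control sites". It introduces the contrast with the two outside clinics with "To obtain an additional non-randomized estimate of the intervention effect, we will compare" and specifies "indicator variables for non-randomized vs randomized clinic, and randomized control vs intervention periods" as model terms.
- The dissemination plan in section V lists a manuscript on "pilot stepped-wedge randomized trial study main effects".

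**The random act.** Section IV.a says "these five clinics will be randomly selected from a total of 28 clinics". Section V.1, step 4.2, says the responsible team member "will randomly select five clinics (from a pool of 27 clinics) as research sites for the study". Both concern which sites enter the study. Step 4.9.1 says that clinics switch from control to intervention, but not how it was decided which clinic switches when.

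**What happened.** The SAP (Study sites and patient eligibility) says that five clinics were originally chosen from a pool of 16, that two randomly selected clinics dropped out once the pilot had started, and that further selected clinics could not take part. Of the three that completed the schedule, "one was randomly selected and two clinics joined based on their capacity to participate in a research study at that time". The SAP's Study design section describes a stepped wedge with three sites and seven 10-week intervals. It does not call the trial randomised.

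**The concern.** Random selection and random assignment do different jobs. Selection bears on whether the clinics represent the health system. Assignment of crossover order bears on whether a difference between intervention and control periods can be attributed to the intervention. In a stepped wedge every clinic moves from control to intervention, so intervention time is always later time. Adjusting for calendar period relies on comparing clinics that have crossed with clinics that have not at the same date, and random order is what makes those comparisons fair.

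The protocol describes only selection, and the SAP shows that selection broke down. Yet the word still labels the analysis groups, model terms and planned main-effects paper. A reader of that paper would give SAP hypotheses 1a and 2a (reach and referrals after against before, in the study clinics) the weight of a randomised comparison. If order was not randomised, secular change is a live alternative explanation, and clinics that crossed early may differ from those that crossed late.

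The SAP's models add to this. Protocol V.c intends to control for calendar time. The SAP's list of possible covariates covers child demographics, preferred language and study site, but no calendar period.

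**Working it through.** The documents give no sample size, power or error rate on this point, so there is no planned figure to reproduce. The check compares texts, with a short count.

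**1. Is the text current?** Both documents have a cover date of 20 July 2024, and the protocol version is dated 10 May 2024. Protocol V.c already allows for COVID-19 and the two outside comparison clinics, and still uses the label. It is current text, not an amendment log.

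**2. What could the word mean?**

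| Sense of *randomized* | What the documents describe | Result for the three analysed clinics |
|---|---|---|
| Randomly selected as a site | Protocol IV.a (pool of 28) and V.1 step 4.2 (pool of 27); the SAP gives a pool of 16 | True for 1, contradicted for 2 |
| Randomly assigned to a crossover step | No text in either document | Undocumented for all 3 |

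Shares: 1/3 = 33% randomly selected; 2/3 = 67% entered on capacity.

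**3. Which estimate does the protocol treat as randomised?** It does not say so outright. It calls the outside-clinic contrast an additional estimate that is non-randomised, so the estimate to which it is added is by implication the randomised one.

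**4. What could random order deliver with this many clinics?** This is an illustration. Assume one clinic per step, because the schedule figure is not available here. With *k* clinics there are *k*! possible orders, and the smallest p-value a randomisation test can reach is 1/*k*!.

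| Case | Possible allocations | Smallest p |
|---|---|---|
| Five clinics, as planned | 5! = 120 | 1/120 = 0.0083 |
| Three clinics, as conducted | 3! = 6 | 1/6 = 0.167 |
| Three clinics, two sharing a step | C(3,1) = 3 | 1/3 = 0.333 |
| Order randomised between two clinics only | 2! = 2 | 1/2 = 0.5 |
| Order not randomised | none | no randomisation basis |

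Even if the order of all three clinics was fully randomised, randomisation alone could not produce a p-value below 0.167. Inference would rest mainly on the model, which makes the missing calendar-period term more important.

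**The case against.** The best defence is that absence from the text is not absence from the trial. No sentence denies that order was randomised. The stepped-wedge schedule and CONSORT figures are not available in the text reviewed, nor is the protocol's timeline table. Protocol V.c also applies the label to periods, which fits randomised timing at least as well as site selection. Clinics that joined on capacity could still have had their order drawn at random. This stands: it would be wrong to conclude that the design lacks randomisation.

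A second defence is disclosure. The SAP reports the losses and the manner of entry, never calls the design randomised, and words hypotheses 1a and 2a as before-after comparisons. This softens the point but does not remove it. The protocol's label is not reconciled with that account, and the SAP does not say what capacity-based entry implies for the status of the estimates.

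Three stronger inferences may tempt a reader. The documents support none of them.
- *The 67% measures bias in the before-after estimate.* It does not. Each clinic serves as its own control there, so manner of entry bears first on representativeness.
- *Capacity-based entry biases hypotheses 1b and 2b in favour of the strategies.* The direction is unknown. The capacity the SAP names is for taking part in research, not for screening. The comparison clinics were themselves chosen because they had begun screening, and they belong to a state-funded project. The protocol already calls this contrast non-randomised.
- *The one randomly selected clinic is a benchmark for the other two.* Random selection gives it no better causal standing, and one clinic cannot show whether manner of entry mattered.

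**Conclusion.** The concern holds, within limits. In the only sense the documents describe, the label is contradicted for two of three analysed clinics. In the sense that would support a randomised causal claim, namely crossover order, it is unsupported by any text. The implied randomised status of the within-clinic estimate therefore has no stated basis.

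The size of any bias cannot be computed from the documents. The conclusion rests on the text of both documents without the figures; a schedule or allocation record showing random order for all three clinics would settle the second half. Hypotheses 1b and 2b are non-randomised either way, with selection bias of unknown direction. The point goes beyond missing detail, because it limits what the trial may claim about the strategies' effect.

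**What to change.** 1. In the SAP, Study design, state whether crossover order was randomly assigned, by what method, and for which of the three clinics.
2. Unless it was randomised for all three, replace *randomized* by *study* for clinics and periods in protocol V.1 step 4.9.2 and V.c (heading, text and model indicators), and drop the word from the main-effects manuscript in the dissemination plan. Present hypotheses 1a and 2a as non-randomised before-after contrasts from a staggered roll-out.
3. Add calendar period to the SAP models for those contrasts, as protocol V.c already intends. Make it a fixed term, not one that depends on the SAP's 15% change-in-coefficient rule. State the assumption of a time trend common to the clinics.
4. State in the SAP that hypotheses 1b and 2b are non-randomised, with selection bias of unknown direction.
5. Report risk differences for reach and referrals for each of the three clinics, marking how each entered, as a descriptive check only.

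The cost is wording in both documents, one model term and one table. Period adjustment with three clinics will probably widen the intervals, and the causal claim becomes weaker if order was not randomised.
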